## **12 DATA HANDLING CONVENTIONS**

All output will be incorporated into Microsoft Word or Excel files, or Adobe Acrobat PDF files, sorted and labeled according to the International Conference on Harmonisation (ICH) recommendations, and formatted to the appropriate page size(s).

All statistical analyses will be 2-tailed and assessed at the 5% significance level. For all analyses except for the CMI data, p-value of < 0.05 will be considered statistically significant. After unblinding, post hoc between treatment comparisons for the CMI endpoints which were exploratory endpoints of the study were performed at 2-sided 0.1 Type I error rate and 2-sided 90% CIs for inference.

Tabulations will be produced for appropriate demographic, baseline, and safety parameters. For categorical variables, summary tabulations of the number and percentage of subjects within each category (with a category for missing data) of the parameter will be presented. For continuous variables, the number of subjects, mean and standard deviation (SD), median, minimum, and maximum values will be presented.

All references to analysis of GMT will be interpreted as analysis of the  $\log_{10}$  of titer values or of the reciprocal titers (eg, the reciprocal titer of 1:160 is the number 160) or of concentrations.

The individual immunogenicity titer values recorded as below the LLoQ of the assay will be set to half LLoQ for the purposes of GMT and GMR analyses, except for the CMI analysis. After unblinding, for the CMI measurements that require log transformation will be assigned a value of 1 count per million cells for those reported as 0. The LLoQ values will be provided by corresponding lab or CRO as part of the data transfer.

Medical history and AEs will be coded using the MedDRA Version 20.0.

Each parameter will be reported with below defined decimal numbers in [Table 7](#).

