10.2 General

Continuous variables will be presented by summary statistics (eg, mean and standard deviation [SD] for the non-immunogenicity endpoints; geometric means and their 95% CI for the immunogenicity endpoints). Categorical variables will be presented by frequency distributions (frequency counts and percentages for the non-immunogenicity endpoints; percentages and their 95% CIs for the immunogenicity endpoints).

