## SAP CHANGE HISTORY

### SAP Version 2.0, 04 March 2020 (revised from Version 1.1, 15 October 2018)

The following is a summary of the changes made to this SAP.

Location of Change	Change/Modification in Version 2.0
Section 8.1.1	Visual Local AE Size Grading Description for 2 – Moderate has been updated from ‘5.0 to 10.0 cm’ to ‘> 5.0 to 10.0 cm’ in Table 4.
Section 12	

Between treatment comparisons for the CMI results were performed at 2-sided 0.1 Type I error rate level and 2-sided 90% CIs for inference.

For the CMI measurements that require log transformation will be assigned a value of 1 count per million cells for those reported as 0 (section 12).

Appendix 1	The table note #9 numbering error has been corrected.

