## 14 CHANGES TO THE SAP

### 14.1 List of Changes from Version 1.1 to Version 2.0

The following changes post unblinding were made to be consistent with previously published data (Couch 2014) from Version 1.1 to Version 2.0 of the Statistical Analysis Plan.

Reason for Changes:

- Between treatment comparisons for the CMI results were performed at 2-sided 0.1 Type I error rate level and 2-sided 90% CIs for inference (Section 12.).
- For the CMI measurements that require log transformation will be assigned a value of 1 count per million cells for those reported as 0 (section 12).

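### After unblinding, the exploratory CMI between-group comparisons were given a 10% level and 90% intervals, while all other analyses stay at 5%

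*SAP*

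**What the plan says.** SAP Section 12 opens with an unqualified rule: "All statistical analyses will be 2-tailed and assessed at the 5% significance level". The next sentence carves out one data type: "For all analyses except for the CMI data, p-value of < 0.05 will be considered statistically significant". The section then says that treatments were compared on these exploratory endpoints once the trial had been unblinded, and it labels those comparisons post hoc. The standard it gives for them is: "performed at 2-sided 0.1 Type I error rate and 2-sided 90% CIs for inference".

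The SAP change history lists this among the revisions from Version 1.1 (15 October 2018) to Version 2.0 (4 March 2020). Section 14.1 gives the reason: "The following changes post unblinding were made to be consistent with previously published data". The publication cited there is a randomised trial of another adjuvanted trivalent influenza vaccine in older adults. The same entry adds a second post-unblinding CMI rule, on how zero counts are log-transformed; that rule is not the subject of this point.

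Protocol Section 10.2 plans "geometric means and their 95% CI for the immunogenicity endpoints" and "percentages and their 95% CIs for the immunogenicity endpoints". It makes no exception for CMI. SAP Section 13, which is reserved for departures from protocol-specified analyses, is marked NA.

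**The concern.** A significance level and an interval width are normally fixed before treatment codes are available. Here one data type received a looser threshold after that point, and the change went in the direction that makes a positive finding easier. The only argument is comparability with an external study. The SAP does not say why that study's level should govern this trial, or why it could not have been adopted before unblinding.

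The CMI objective in both documents is to describe responses, so it does not call for a 10% test, and using the intervals for inference goes beyond description.

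What is at stake is the reading of borderline contrasts. A CMI contrast with p between 0.05 and 0.10 can be called significant, while an HAI or microneutralization contrast with the same p cannot. SAP Section 9 says the remaining immunogenicity analyses serve to choose the dose and formulation for the next study from all available results. CMI can therefore contribute to that choice, although no decision rule is tied to it.

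**Working it through.** **Inputs.** CMI level 0.10 with 90% intervals, and the general 5% level (SAP Section 12). Immunogenicity intervals at 95% (Protocol 10.2). About 189 CMI subjects, drawn from Stage 3, with a target of at least 20 evaluable per group (Protocol 6.1.2). Stage 3 allocation of 115 in Groups A, C, D, F and G and 230 in Groups B and E, total 1035 (Protocol Table 1). No multiplicity adjustment for these analyses (SAP Section 9).

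**Step 1: reproduce the plan's figures.** Alpha = 1 − confidence level. For CMI, 1 − 0.90 = 0.10, so the SAP's level and interval agree with each other. For the rest, 1 − 0.95 = 0.05. The power table (SAP Table 6) also rests on 2-sided 5%. With n = 295 per group, SD 0.6 and a 1.4-fold ratio, log10(1.4) = 0.1461 and SE = 0.6 × √(2/295) = 0.0494. The ratio is 2.958, and Φ(2.958 − 1.960) = 84.1%, against the stated 84%.

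**Step 2: false-positive rate per contrast.** 0.10/0.05 = 2.00. The doubling is exact for the nominal rate of a single contrast.

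**Step 3: CMI group sizes.** If the subset follows the Stage 3 allocation, 189 × 115/1035 = 21 in A, C, D, F and G, and 189 × 230/1035 = 42 in B and E. Both fit the target of at least 20.

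**Step 4: interval width.** Half-width = quantile × SE, so the SE cancels in the ratio of the 90% width to the 95% width.

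| Basis | 90% quantile | 95% quantile | Ratio |
|---|---|---|---|
| Normal | 1.645 | 1.960 | 0.839 |
| t, 20 vs 20 (38 df) | 1.6860 | 2.0244 | 0.833 |
| t, 21 vs 42 (61 df) | 1.6702 | 1.9996 | 0.835 |
| t, 42 vs 42 (82 df) | 1.6636 | 1.9893 | 0.836 |

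The 90% intervals are 16-17% narrower. Conversely, the 95% intervals are 1.19 to 1.20 times as wide.

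**Step 5: several contrasts (illustration only).** The plan gives no count of CMI contrasts. For k independent contrasts, the chance of at least one false positive is 1 − (1 − α)^k.

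| k (assumed) | α = 0.05 | α = 0.10 |
|---|---|---|
| 3 | 14.3% | 27.1% |
| 6 | 26.5% | 46.9% |
| 10 | 40.1% | 65.1% |

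The rise is less than twofold for every k above 1. The contrasts would not be independent, because the three cytokines come from the same subjects and many comparisons share a group.

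**The case against.** The sponsor has a reasonable case. The change is disclosed in the change history, in Section 12 and in Section 14.1. It is labelled post hoc and exploratory, and a reason is given. The cited publication is not available here, so the strength of that reason cannot be fully judged. The subset is small, and a looser level recovers some power: for an assumed true difference of 0.5 SD with 21 per group, power is 35% at the 5% level and 48% at the 10% level. A reader can also approximate a 95% interval by widening the 90% one by about a fifth. All of this lowers the severity. It does not explain why the level was set only after unblinding, and no 95% interval is planned alongside.

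Four stronger readings are tempting, and the documents do not support them:

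- **That a planned 5% CMI test was loosened.** The text of Version 1.1 is not available. Section 12 calls the comparisons themselves post hoc. The group differences listed in Protocol 10.4.2 are for HAI and neutralization endpoints, and SAP Section 7.3 names no CMI contrast. Version 1.1 may have planned no formal CMI comparison at all.
- **That the level was chosen with CMI results in view.** The text says only that it was after unblinding. Under Protocol 10.6.1 and SAP Section 10, only a select group was to be unblinded at Day 28, with the immunology laboratory kept blinded, and CMI data could be held for the final report. The past tense in Section 12 suggests that the comparisons had been run by Version 2.0, but it does not fix the order of events.
- **That intervals throughout the trial became narrower.** Only the CMI between-group intervals change.
- **That the adjuvant-effect conclusion is affected.** That objective is defined by Day 28 HAI, Group B versus Group E, and stays at 5%.

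**Conclusion.** The point holds in a limited form. After unblinding, the SAP applied a threshold to the CMI between-treatment comparisons that is looser than its own general rule and than the protocol's interval level. Relative to the 5%/95% convention, the nominal error rate per contrast doubles and the intervals are about 16-17% narrower. The doubling and the normal-quantile ratio need no assumption; the t-based ratios assume group sizes of about 20 to 42. Any family-wise figure rests on an assumed number of independent contrasts and should not be cited as a property of this trial.

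Severity is low to moderate. No primary, secondary HAI or microneutralization result changes. The risk is that borderline exploratory CMI contrasts are described as significant and carry more weight in choosing a formulation than the same evidence would carry elsewhere in the trial.

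**What to change.** In SAP Section 12, report the CMI between-group comparisons with 2-sided 95% intervals and judge them at the general 5% level. Keep the 90% intervals only as a supplement labelled post hoc, with no significance statements attached. This would also remove the conflict between the unqualified opening rule of Section 12 and the exception that follows it.

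Replace the NA in Section 13 with an entry stating that between-treatment CMI comparisons were added after unblinding, the level that was used, and the reason.

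The cost is a wording change and a re-run of the CMI tables; no new data are needed. The downside is CMI intervals about 1.2 times as wide and possibly fewer contrasts called significant. It also means one more SAP edit after unblinding, but this one returns to the trial's general convention.

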**Table 7: Decimal Numbers for Parameters**

Parameter	Number of Decimals
Number of subjects (e.g. N, N1, N2)	0
Percentage (%)	1
Mean	1 more decimal than raw data
Standard Deviation (SD)	1 more decimal than mean
Median, Min, Max	as same decimal as raw data
GMT, GMR Post/Pre , their corresponding 95% CIs	1
Ratio of GMTs, its corresponding 95% CIs	2
SPR (%), SCR (%), SPR difference, SCR difference, their corresponding 95% CIs	1
P value for GMR Post/Pre and Ratio of GMTs	3

Note: For analysis of exploratory CMI response, up to 5 decimal numbers will be presented depending on number of significant digits for each parameter.

## 12.1 Baseline Definitions

For all analyses, baseline will be defined as the last non-missing measurement prior to the first administration of the study material. For immunogenicity analysis, baseline will be the sample drawn prior to the first vaccination, on the day of vaccination.

## 12.2 Adjustments for Covariates

Comparison of GMTs between treatment groups will be adjusted for pre-vaccination titer.

## 12.3 Multiple Comparisons/Multiplicity

No multiplicity adjustment will be applied for the secondary endpoints.

## 12.4 Withdrawals, Dropouts, Loss to Follow-up

The Investigator may withdraw any subject from the study at any time for medical reasons or if the subject is unable or unwilling to comply with the protocol. A subject may elect to discontinue his/her participation and withdraw from the study at any time. A subject withdrawing from the study may do so without detriment to access to medical care. See Sections 6.5 - 6.6 of the protocol for more details on withdrawal of subjects.

Any subject discontinuing from the trial at any time other than the screening period will not be replaced. A subject who receives the investigational product but withdraws for any reason will be encouraged to return for the safety assessments according to the Schedule of Procedures ([Appendix 1](#)). If the subject does not wish to remain in the study, the subject can choose to withdraw consent and discontinue at any time as outlined in Section 6.5 of the protocol.

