6.4 Declining Trial Treatments or Procedures

Subjects have the right to decline trial treatment or other trial procedures for any reason at any time during the trial. This trial contemplates at least 2 injections containing either Quad-NIV with or without Matrix-M1 adjuvant, Fluzone HD, Flublok Quadrivalent, or saline placebo. Refusal of the investigational test article on Day 0 constitutes trial withdrawal without exposure, and no further follow-up is required. If a subject declines trial procedures subsequent to receipt of the investigational product, it should be recorded as a protocol deviation and the reason should be clearly documented in the source document. The subject will be asked to complete all other trial procedures as applicable. If the subject does not wish to remain in the trial, the subject can choose to withdraw consent and discontinue at any time as outlined in Section [6.5](#).

The investigator may, at his/her discretion, restrict a subject from receiving trial treatment or other trial procedures if he/she considers it to be in the subject's best interest to do so, but can suggest that the subject remain in the trial to be followed for safety if the subject has received a test article. In this situation, the reason for not performing the trial treatment and/or procedure should also be recorded as a protocol deviation and clearly documented in the source document.

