6.5 Premature Discontinuation from Trial

Subjects who provide consent but are found to be ineligible on screening will be informed of the reason for ineligibility and may be provided with local medical referral by the investigator as appropriate, but will receive no further trial follow-up.

Subject participation in the trial is strictly voluntary. Subjects have the right to withdraw from the trial at any time and for any reason, without penalty. The investigator may also, at his/her discretion, discontinue subjects from the trial if he/she considers it to be in the participant's best interest to do so, or if the subject is not willing or able to comply with the trial requirements. Novavax will be notified immediately by the investigator if a subject prematurely ends trial participation. The reason for early discontinuation will be clearly documented in the electronic case report form (eCRF). A withdrawal due to an AE will initiate additional reporting requirements as outlined in Section [8.3](#).

In the event of early termination, investigators will make every reasonable effort to perform trial completion procedures. Trial completion procedures will include a query for any MAEs, SNMCs, or SAEs occurring since the last trial visit, and any concomitant medications taken to treat these events. If the subject discontinues from the trial prior to the Day 28 visit, sites will request the subjects to provide blood samples for serology testing (20 mL) and clinical safety laboratory testing (10 mL). Subjects that terminate from the trial early will not be replaced.

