### 8.1 Analyses of Primary Objectives of Safety

Safety analysis will be descriptive and based on the safety population, defined as all subjects who received a dose of trial treatment. Safety data will be summarized overall and by individual treatment group for solicited short-term reactogenicity events on Day 0-6, all unsolicited AE profile by MedDRA preferred term and SOC, and 1-year MAE, SAE, and SNMC profiles post-injection on Day 0. All AEs, including MAEs, SAEs, and SNMCs, will be tabulated by severity, related (possibly, probably, or definitely vs. non-related per investigator assessment), and severe and related. The number and percentage (with 2-sided exact 95% CI) of subjects in each treatment group with a given term will be summarized. A listing and narratives of SAEs will also be produced. For multiple occurrences of an adverse event in the same subject, a subject will be counted only once, using the most severe or most related occurrence for the summarization by severity or relationship to test article, respectively.

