## **8.2 Medically-Attended Events and Significant New Medical Conditions**

These classes of events will be collected at all study visits, and if offered spontaneously by the subject at any time.

Medically-attended events (MAEs) are adverse events which result in an unscheduled visit to a healthcare provider due to symptomatic illness or injury. These may include office visits, clinic visits, home consultations, or emergency room evaluations for non-life-threatening events that do not result in hospitalization (life-threatening events or hospitalizations are SAEs, see Section 8.3).

Significant new medical conditions (SNMCs) are adverse events that are new (that is, not present at baseline), clinically significant (meaning that they imply an important change in the subject's long-term health status), and typically chronic (requiring an ongoing change in the subject's medical management). This category is not meant to include minor or transient diagnoses or age-related changes.

The eCRF will provide a field in which the investigator may designate AEs as MAEs, SNMCs, or both. Because of the significance of the designation for the subject's health, long-term medical management, and for evaluation of vaccine safety, SNMCs are expected to be substantiated diagnoses, not isolated symptoms which might or might not be a SNMC, and the investigator should record sufficient data in the eCRF to support the diagnosis.

Full details of MAEs and SNMCs (ie, nature, date of onset, and recovery (if applicable) as well as an assessment of severity, relationship to trial agent, seriousness, treatment, and outcome) will be recorded in the source documentation and captured in the eCRF, and will require the investigator(s) causality assessment.

MAEs and SNMCs will be recorded and summarized from Day 0 to Day 28 for the unblinded data review and from Day 0 to Day 364 following study completion for the final analysis, for all subjects in the Safety Population. Note that MAEs and SNMCs are also included in the overall summary of AEs.

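### The one-year MAE, SNMC and SAE percentages make no allowance for follow-up lost after withdrawal, and SAP 12.4 and protocol 6.5 differ on what safety follow-up leavers are offered

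*SAP*

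**What the plan says.** **Follow-up after withdrawal.** SAP 12.4 says of dosed subjects: "A subject who receives the investigational product but withdraws for any reason will be encouraged to return for the safety assessments", following the schedule in its Appendix 1. It refers to protocol 6.5 and 6.6 for detail. It then adds: "If the subject does not wish to remain in the study, the subject can choose to withdraw consent and discontinue at any time", again pointing to protocol 6.5.

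Protocol 6.5 reads: "In the event of early termination, investigators will make every reasonable effort to perform trial completion procedures". It defines these as follows: "Trial completion procedures will include a query for any MAEs, SNMCs, or SAEs occurring since the last trial visit", together with medications taken for those events. It also says: "If the subject discontinues from the trial prior to the Day 28 visit, sites will request the subjects to provide blood samples", for serology and safety laboratory tests. It describes no later safety contact, and leavers are not replaced.

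Protocol 6.4 concerns subjects who decline procedures, or are restricted from them, but remain in the trial. Of those who decline it says: "The subject will be asked to complete all other trial procedures as applicable".

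**Analysis.** The Safety Population (SAP 3.1) is everyone consented, randomized and dosed, with no follow-up requirement. SAP 8.1 sets the statistic: "The number and percentage (with 2-sided exact 95% CI) of subjects in each treatment group with a given term will be summarized". For MAEs and SNMCs, SAP 8.2 sets the window and denominator: "from Day 0 to Day 364 following study completion for the final analysis, for all subjects in the Safety Population". SAP 8.3 uses the same window and population for SAEs. SAP 12.5 makes no general substitution for missing data. Neither document mentions censoring, person-time or a denominator based on observed follow-up.

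**The concern.** The one-year MAE, SNMC and SAE profile, including adverse events of special interest, is part of a primary objective, in the first human exposure to Quad-NIV with Matrix-M1. Two things bear on how well the plan can describe it.

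First, the SAP appears to assume safety data after withdrawal that the protocol, which sites follow, gives no instruction to collect. This matters most for subjects whom the investigator discontinues, for example for not complying with trial requirements. They need not have refused further contact.

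Second, if those data stop at exit, a fixed denominator of all dosed subjects gives a percentage that falls as withdrawal rises. Every arm is then biased downward, and arms with more withdrawal are biased more. A comparison of adjuvanted and comparator arms would carry part of any difference in dropout.

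**Working it through.** **1. The plan's own safety figures (SAP 9).** P(at least one event) = 1 − (1 − p)^n. The zero-event one-sided 95% upper bound is 1 − 0.05^(1/n).

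| n | p | P(≥1), recomputed | Stated | Bound, recomputed | Stated |
|---|---|---|---|---|---|
| 135 | 1.7% | 90.1% | > 90% | 2.19% | 2.2% |
| 155 | 1.5% | 90.4% | > 90% | 1.91% | 1.9% |
| 310 | 0.8% | 91.7% | > 90% | 0.96% | 1.0% |

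All reproduce, on the basis that every dosed subject is fully observed. SAP 9 does not tie these figures to one-year events. If they are applied to such events with 5% uniform withdrawal (assumed), the effective n is n × (1 − 0.05/2) = 131.6, 151.1 and 302.2. The probabilities become 89.5%, 89.8% and 91.2%.

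**2. Inputs for the one-year percentages.**
- Denominator and statistic: SAP 3.1, 8.1, 8.2 and 8.3.
- One-year withdrawal share w: not given. The only stated attrition is 5% for the per-protocol population (SAP 9). I assume 2% and 10%.
- True one-year risk p: not given. I assume 40% and 20% for MAEs. For SAEs I use 5.5%, within the 5.4% to 6.4% by arm reported for the earlier trial (protocol 1.8.1). Follow-up there was still running, so this sets a scale and is not a one-year risk.
- Constant hazard, and withdrawal unrelated to event risk: assumed.

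**3. Formulas.** Hazard h = −ln(1 − p) per year. The observed risk of a leaver is q = 1 − p/h if exits are uniform over the year, or q = 1 − exp(−h/13) if all leave at Day 28 (28/364 = 1/13). The crude percentage is (1 − w)p + wq.

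Worked case, p = 40%, uniform exits: h = 0.5108 and q = 1 − 0.40/0.5108 = 0.2170. With w = 10%, 0.90 × 0.40 + 0.10 × 0.2170 = 38.17%. With w = 2%, 0.98 × 0.40 + 0.02 × 0.2170 = 39.63%.

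| True risk | Uniform, w = 2% | Uniform, w = 10% | False difference (points) | All at Day 28, w = 2% | All at Day 28, w = 10% | False difference (points) |
|---|---|---|---|---|---|---|
| 40% | 39.63% | 38.17% | 1.46 | 39.28% | 36.39% | 2.89 |
| 20% | 19.81% | 19.04% | 0.77 | 19.63% | 18.17% | 1.46 |
| 5.5% | 5.45% | 5.23% | 0.22 | 5.40% | 4.99% | 0.41 |

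The relative understatement is w(1 − q/p). Across these risks it is 0.46w to 0.50w for uniform exits and 0.90w to 0.92w if all leave at Day 28. The Day 28 case is an extreme bound.

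**4. Against sampling error.** The 95% half-width for a difference at 40% is 1.96 × √(2 × 0.24/155) = 10.9 points for 155 against 155, and 1.96 × √(2 × 0.24/310) = 7.7 points for 310 against 310. At 5.5%, for 310 against 155, it is 1.96 × √(0.055 × 0.945 × (1/310 + 1/155)) = 4.4 points. The bias is well inside these widths, although it is systematic.

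**5. Does person-time remove it?** Expected time to first event, withdrawal or year end is p/h for stayers and q/h for leavers. At p = 40% and w = 10%: 0.90 × 0.7830 + 0.10 × 0.4247 = 0.7472 years. The rate is 0.3817/0.7472 = 0.511 per person-year, equal to h. At w = 2% it is 0.3963/0.7759 = 0.511. Under the stated assumptions the rate does not depend on withdrawal.

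**The case against.** **The wording mismatch may be loose drafting.** SAP 12.4 takes the same two steps as protocol 6.4: continue with what the subject will still accept, and if the subject does not wish to remain, go to 6.5. Its second step is almost the protocol's own sentence. On that reading, withdrawal in the SAP means declining further treatment or procedures. This is plausible. However, the SAP sentence covers withdrawal for any reason and cites protocol 6.5 and 6.6, not 6.4, so the literal difference still needs resolving.

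**Protocol 6.5 does not forbid later contact.** A reader might infer that it ends follow-up with a single query. The text does not support that. It says what completion procedures include, adds blood samples before Day 28, and is silent on later contact. MAEs and SNMCs are also collected whenever a subject volunteers them (protocol 8.1.5).

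**Leavers are not simply counted as event-free.** A reader might infer this from the denominator, but events before exit, and those found at the completion query, enter the numerator. Only later time is lost.

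**Dropout will be visible.** SAP 4 tabulates discontinuations and reasons by arm and lists the day of last study contact. That lets a reader see unequal follow-up, but it does not adjust the percentages.

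**The percentage is the protocol's defined endpoint, and safety is descriptive.** Both are true. The SAP implements the endpoint faithfully, so an exposure-adjusted rate is a supplement to it and not the repair of an error.

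**Conclusion.** The point stands at low severity. Read literally, SAP 12.4 describes safety follow-up after withdrawal that protocol 6.5 does not provide for, and protocol 6.4 covers only subjects who stay. The one-year percentages carry a downward bias that grows with withdrawal, because the denominator is fixed and no account is taken of observed time.

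The false difference is about 0.2 points at an SAE-like 5.5% and about 1.5 points at an MAE risk of 40%, for 10% against 2% uniform withdrawal. It roughly doubles in the extreme case where every leaver goes at Day 28. These figures rest on assumed withdrawal shares and MAE risks, a constant hazard, and withdrawal unrelated to risk.

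It would go too far to conclude that the one-year safety comparison is invalid, or that unequal dropout is likely to mask or create a safety signal. The documents give no one-year withdrawal rate and no reason to expect unequal withdrawal, and no between-arm safety test is planned. The Day 28 immunogenicity comparison of Groups B and E is not affected.

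**What to change.** 1. **SAP 8.2 and 8.3.** For the Day 0 to 364 MAE, SNMC and SAE summaries, add for each arm the person-time and the exposure-adjusted incidence beside the crude percentages. Define it as subjects with a first event per person-year, censored at last study contact. SAP 4 already derives day of last contact for discontinued subjects, so no new data are needed. That derivation uses the recorded discontinuation date, so state how subjects lost to follow-up are handled if that date falls after the last actual contact.

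2. **SAP 12.4 with protocol 6.4 and 6.5.** Reconcile these sections on what safety follow-up is sought from dosed subjects who are discontinued but have not withdrawn consent to contact, and use one meaning of withdrawal throughout.

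The cost is one extra column in the one-year safety tables and a wording correction. The rate relies on withdrawal being unrelated to event risk, so it removes the mechanical effect of lost time but not bias from subjects leaving because they are unwell. The crude percentages remain as the protocol's defined endpoint.
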